10 Within 7 days prior to first dose of investigational product (central laboratory assessment).

11 Training on Worst Itching Intensity NRS will be conducted on the first day of the run-in period (Day -7).

- 12 Training on Skindex-10 scale and 5-D itch scale may be performed at any time during the week prior to randomisation or on Day 1 of the double-blind period.
- 13 Subjects will be requested to complete their Worst Itching Intensity NRS worksheets each day at a similar time (either at home on non-dialysis days around the normal start time of their dialysis or in the dialysis unit). On dialysis days, the worksheets will be completed prior to or during dialysis, but must be completed prior to dosing.
- 14 During the follow-up period, Worst Itching Intensity NRS worksheets will be completed on dialysis days only.
- 15 5-D itch scale and Skindex-10 scale will be completed on Day 1 and the first visit of Week 5 (Day 29), Week 9 (Day 57) and Week 13 (Day 85). 5-D itch scale will preferably be completed first. If the first visit of the week is missed, the subject may complete the worksheets at their next visit for the same week. The worksheets will be completed prior to or during dialysis (preferably within 1 hour of the dialysis) but must be completed prior to dosing.
- 16 Concomitant medications including antipruritic medication will be updated at each dialysis visit during the double-blind period, and until the end of the follow-up period.
- 17 A list of specific signs/symptoms will be verified with the subject by qualified site staff, preferably to be completed on Wednesday/Thursday each week during the run-in period, the double-blind period, and the discontinuation period. Not to be completed on Monday/Tuesday (see Section 10.8.4.1 for a list of the AESIs).

Notes: AESI=Adverse event of special interest; ALT=Alanine aminotransferase; AST=Aspartate aminotransferase; BUN=Blood urea nitrogen; ECG=Electrocardiogram; eCRF=Electronic Case Report Form; EoT=End of treatment; F=Friday; IV=Intravenous; M=Monday; MCH=Mean corpuscular haemoglobin; MCHC=Mean corpuscular haemoglobin concentration; MCV=Mean corpuscular volume; NRS=Numerical Rating Scale; PRO=Patient reported outcome; RDW=Red blood cell distribution width; S=Saturday; SGOT=Sersum glutamic-oxaloacetic transaminase; SGPT=Sersum glutamic-pyruvic transaminase; Th=Thursday; Tu=Tuesday; W=Wednesday.

Table 2 Schedule of Events and Assessments for the Open-label Extension Period

Study Procedures	Open-label Treatment Period ⁽¹⁾							EoT/ Early Termination	Follow-Up
	Day 1 ⁽²⁾	Week 2 ⁽¹⁾	Week 4 ⁽¹⁾	Week 6 ⁽¹⁾	Week 8 ⁽¹⁾	Week 10 ⁽¹⁾	Week 12 ⁽¹⁾		
Inclusion/exclusion criteria	X ⁽⁵⁾								
Physical examination	X								
Prescription dry body weight ⁽⁶⁾	X						X		
Pre-dialysis 12-lead electrocardiogram ⁽⁷⁾								X	
Pre-dialysis vital signs ⁽⁸⁾	X		X		X		X	X	X
Haematology, serum chemistry (pre-dialysis)								X	
Serum potassium (pre-dialysis)		X	X	X	X	X	X		
Serum pregnancy test for women of childbearing potential only								X	
5-D itch scale, Skindex-10 scale ⁽⁹⁾			X		X		X	X	
IV administration of investigational product	After each dialysis, up to Week 14 included								
Adverse event monitoring	Record on an ongoing basis ⁽¹⁰⁾								
Concomitant medications (including antipruritic medications)	Record on an ongoing basis ⁽¹⁰⁾								

- 1 Each visit during the open-label treatment period will coincide with the subject's normal dialysis treatments. The study visit may occur on any chosen dialysis day of a scheduled week if all assessments are completed during that visit.
- 2 Day 1 of the open-label treatment period corresponds to the day of the last visit of the double-blind period or up to 1 week following the double-blind period.
- 3 The end-of-treatment visit will be the first dialysis visit following the last dose of investigational product (i.e., first dialysis on Week 15).
- 4 The follow-up visit will coincide with a dialysis day.
- 5 Prior to dosing on Day 1 of the open-label treatment period, the inclusion/exclusion criteria will be confirmed.
- 6 The prescription dry body weight will be captured from the dialysis prescription and will be recorded on Day 1 and at Week 12. If there is a >10% change in prescription dry body weight compared to the last value, then the difelikefalin dose will be adjusted.
- 7 Electrocardiogram must be performed prior to the start of dialysis.

- 8 Vital signs, including body temperature, heart rate, and blood pressure, will be obtained at the specified visits while the subject is in a sitting or semi-recumbent position prior to the start of dialysis. Heart rate will be measured at each dialysis; if the heart rate is clinically significant at visits outside the pre-specified visits per Schedule of Events, the heart rate will be recorded in the eCRF.

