--

[figure not shown]
	
The first visit and first dosing for the open-label extension phase of the study will occur immediately on the day of the last visit of the double-blind period or up to 1 week following the double-blind period. Day 1 of the open-label extension period will be defined as the day of administration of the first dose of difelikefalin in the open-label extension period and will occur preferably on the first dialysis session of the first treatment week (i.e., Monday for subjects on a Monday-Wednesday-Friday dialysis schedule, or Tuesday for subjects on a Tuesday-Thursday-Saturday dialysis schedule).
 
The last dose of open-label difelikefalin will be administered at the last dialysis visit on Week 14, or early termination.
 
Subjects will complete the Skindex-10 scale and 5-D itch scale at Week 4, Week 8, Week 12 and at the end-of-treatment visit, which corresponds to the first dialysis visit following the last dose of difelikefalin given in the open-label extension (i.e., first dialysis on Week 15).
 
Blood samples for clinical laboratory tests will be collected at the end of treatment or early termination visit; in addition, blood samples for analysis of serum potassium will be collected every 2 weeks (on dialysis days), i.e., at Week 2, Week 4, Week 6, Week 8, Week 10 and Week 12 of the open-label extension. Vital signs will be monitored on Day 1, at Week 4, Week 8, Week 12 and at the end of treatment or early termination visit. AEs and concomitant medications will be continuously recorded throughout the open-label treatment period.
 
12-lead ECGs will be monitored at the open-label end of treatment or early termination visit.
 
Follow-up Period
 
A final safety follow-up visit will be conducted in 7 to 10 days:
 
 • After the end-of-treatment visit of the double-blind period for subjects not participating in the open-label extension phase • After the end-of-treatment visit of the open-label extension period for subjects participating in the open-label extension phase • Or after the early termination visit during either the double-blind period or the open-label extension phase

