3 The end-of-treatment visit in the double-blind phase will be the first dialysis visit following the last dose of investigational product (i.e., first dialysis on Week 13 (Day 85)), which also corresponds to Day 1 of the first day of the open-label extension. For subjects not participating in the open-label extension, Day 85 corresponds to Day 1 of the follow-up period.

4 Medical history will be updated on Day 1 with any changes since the screening visit, and inclusion/exclusion criteria will be confirmed prior to randomisation. Antipruritic medication will be updated at each dialysis visit during the run-in period.

5 12-lead ECG must be performed prior to the start of dialysis at screening, Day 85 (double-blind period end of treatment), or at early termination visit.

6 Pre-dialysis vital signs, including body temperature, heart rate, and blood pressure, will be recorded on Days 1, 15, 29, 43, 57, 71 and 85 (double-blind period end of treatment), or at early termination visit only when the subject is in a sitting or semi-recumbent position. Heart rate will be measured at each dialysis; if heart rate is clinically significant at visits outside the pre-specified visits per Schedule of Events, the heart rate will be recorded in the eCRF.

7 Pre-dialysis vital signs, including body temperature, heart rate, and blood pressure, will be recorded at the follow-up visit (at 7 to 10 days after EoT/ET visit). Heart rate will be measured at each dialysis visit during the follow-up period; if heart rate is clinically significant at visits outside the follow-up visit, the heart rate will be recorded in the eCRF.

8 Blood samples for clinical laboratory evaluation will be taken at screening, and on Days 1 and 85 (double-blind period end of treatment), or at early termination visit only and will be assessed at central laboratory. Haematology will include basophil %, basophil (absolute), eosinophil %, eosinophil (absolute), haematocrit, haemoglobin, lymphocyte %, lymphocyte (absolute), MCH, MCHC, MCV, monocyte %, monocyte (absolute), neutrophil %, neutrophil (absolute), platelet, RDW, red blood cells, white blood cells. Serum chemistry will include albumin, alkaline phosphatase, ALT/SGPT, AST/SGOT, bilirubin (total), BUN, calcium, chloride, creatinine, glucose, phosphorus, potassium, sodium.

9 Serum potassium will be assessed separately at Weeks 3, 5, 7, 9 and 11 (Days 15, 29, 43, 57 and 71) (central laboratory assessment).

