8.7.2 Week 2/Open-label Extension

The study visit may occur on any chosen dialysis day of a scheduled week as long as all assessments are completed during that visit. The following assessments will take place:

- Assessment of serum potassium before starting of dialysis (central laboratory)
- IV administration of difelikefalin (within 15 minutes after completion of dialysis session)
- AE assessment on an ongoing basis
- Concomitant medications (including antipruritic medications) recorded on an ongoing basis

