9.2 Physical Examination and Vital Signs

Physical examination will include general appearance, cardiovascular, respiratory, abdominal, musculoskeletal, neurological, lymph nodes, and skin. Any findings at screening should be reported in the medical history; clinically significant changes should be reported as AEs.

Vital signs will include oral body temperature (°C), respiratory rate, radial pulse rate, systolic and diastolic blood pressures. Sitting recordings are to be made after the subject has been sitting for at least 5 minutes with their feet squarely on the floor and arms relaxed, bent at the elbow.

An AE form must be completed for all changes identified as clinically noteworthy.

9.3 12-lead ECG

Standard 12-lead ECGs will be measured after the subject has been resting for minimum of 5 minutes.

All 12-lead ECG recordings (including heart rate, QT, QTcF, QTcB, RR interval, P-wave, QRS complex duration and PR interval) will be performed and interpreted at study sites by Investigators. ECGs will be planned to coincide with first dialysis of the week. If this is not possible, ECGs should be planned for the same session of the week.

At screening, the Investigator must document clinically relevant ECG findings on the appropriate baseline eCRF pages and in the subject's hospital records. Any new clinically relevant ECG finding, or aggravation/worsening of an already existing finding as assessed by the Investigator, must be reported as an AE (see Section 10).

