4.8.2 Clinical Laboratory Evaluations

Subject clinical laboratory evaluations including serum chemistry, haematology and potassium will be summarized descriptively using central laboratory.

Laboratory values will be reported in units according to the International System of Units as per [Appendix 2](#) in the SAP.

Summaries of actual values and the change from baseline to each time point (when applicable) including last post-baseline measurement will be presented for quantitative laboratory parameters. Descriptive statistics are calculated by treatment sequence and all sequences pooled on both the actual values and the change from baseline.

Baseline is defined as the last measurement taken on or prior to the first day of open-label dosing. This will typically be the end of treatment visit for the double-blind period.

Laboratory test results will be classified according to whether the value was below (L), within (N), or above (H) the laboratory parameter reference range. A summary of shifts will compare the baseline L/N/H classification for each laboratory test to the L/N/H classification at end of open-label extension period and at last post-baseline. For serum potassium, shift table comparing the baseline L/N/H classification to each post baseline L/N/H classification (including last post-baseline) will also be provided.

All laboratory results will be listed, including data at any unscheduled visits. In addition, all abnormal (with classification of L or H) laboratory values will be presented in a separate listing.

4.8.3 12-lead Electrocardiogram (ECG) Evaluations

Summary tables for 12-lead ECG include descriptive statistics for baseline and each post baseline assessment including last post-baseline measurement during the open-label extension period. Descriptive statistics are calculated by treatment sequence and all sequences pooled on both the actual values and the change from baseline for Heart Rate, QT interval, QTcF interval, QTcB interval, RR interval, P-wave, QRS complex duration and PR interval. Overall interpretation of the 12-lead ECG readings is to be tabulated as well by treatment sequence and all sequences pooled at baseline, at end of open-label extension period and at last post-baseline assessment.

Baseline is defined as the last measurement taken on or prior to the first day of open-label dosing. This will typically be the end of treatment visit for the double-blind period.

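### Open-label potassium at Weeks 2 to 12 is not tied to the dialysis session of its baseline, so the interim by-visit changes and shifts may be biased, probably downward

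*Protocol*

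**What the plan says.** **Open-label draws.** Protocol Table 2, footnote 1: "The study visit may occur on any chosen dialysis day of a scheduled week", provided that all assessments are done at that visit. Sections 8.7.2 to 8.7.7 repeat this for Weeks 2, 4, 6, 8, 10 and 12, each with a pre-dialysis central-laboratory potassium. The synopsis (Procedures) is no tighter: "blood samples for analysis of serum potassium will be collected every 2 weeks (on dialysis days), i.e., at Week 2, Week 4", and so on to Week 12.

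**Baseline.** Table 2 has no potassium draw on open-label Day 1. SAP 4.8.2 takes the last measurement on or before the first open-label dosing day and adds: "This will typically be the end of treatment visit for the double-blind period". Protocol Table 1, footnote 3, places that visit at the "first dialysis on Week 13 (Day 85").

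**Analysis.** SAP 4.8.2 summarises potassium values and changes from baseline at each time point, and cross-tabulates the baseline low/normal/high class against each post-baseline class. The visit windows (SAP Table 3) and the selection rule (SAP 4.1.3) work by day and visit type, not by dialysis session.

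**Contrast.** For ECGs, Protocol 9.3 says "ECGs will be planned to coincide with first dialysis of the week", and failing that asks for the same session of the week each time.

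**The concern.** On the Monday-Wednesday-Friday and Tuesday-Thursday-Saturday schedules that the protocol names, the first session follows a 3-day gap and the other two follow 2-day gaps. If pre-dialysis potassium is higher after the longer gap, comparing a first-session baseline with later-session follow-up builds in a fall that has nothing to do with treatment, and could offset part or all of a real rise.

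Potassium is the only laboratory parameter sampled every 2 weeks. Protocol 1.2.2.2 lists hyperkalaemia among both the common adverse events and the common serious adverse events that were more frequent than on placebo in haemodialysis subjects. The extension exists partly to collect more safety data (Protocol 2.2). It has no concurrent placebo arm that would reveal a timing artefact.

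**Working it through.** The plan states no figure on this point, so there is none to reproduce. The check has a calendar part, which rests on the documents, and a size part, which rests on assumptions.

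**1. Calendar.** A study day falls on the same weekday as Day 1 when (day - 1) is a multiple of 7.
- Double-blind potassium (Table 1, footnotes 8 and 9), Days 15, 29, 43, 57, 71 and 85: (day - 1)/7 = 2, 4, 6, 8, 10 and 12. All share the weekday of Day 1.
- Open-label end of treatment, target Day 99 (SAP Table 3): (99 - 1)/7 = 14. It shares the weekday of open-label Day 1.
- Open-label Weeks 2 to 12: any dialysis day of the week.

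The double-blind series and the end-of-treatment comparison are therefore session-matched on the planned schedule. Only the six interim visits are free.

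**2. Mean change.** Let d be the excess of potassium after the 3-day gap over that after a 2-day gap (mmol/L), and q the share of interim draws at a 2-day-gap session. With baseline at the 3-day-gap session, bias = -q × d. The documents give neither d nor q. Assume d = 0.2 to 0.6.

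| q | d = 0.2 | d = 0.4 | d = 0.6 |
|---|---|---|---|
| 0 (always first session) | 0 | 0 | 0 |
| 2/3 (even spread) | -0.13 | -0.27 | -0.40 |
| 1 (never first session) | -0.20 | -0.40 | -0.60 |

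The sign depends on the baseline session. If a subject's Day 1, and so Day 85, falls at a 2-day-gap session, then bias = +(1 - q) × d. At q = 2/3 and d = 0.2 to 0.6 that is +0.07 to +0.20.

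**3. Shifts.** For illustration, take baseline and follow-up as bivariate normal with first-session mean 5.0, SD 0.7, correlation 0.6 and upper limit 5.3 mmol/L. All four values are assumed. Among subjects not high at baseline, the share shifting to high is (1 - q) × matched share + q × share with the follow-up mean lowered by d. For d = 0.2, q = 2/3 and no true change: (1/3) × 20.1% + (2/3) × 12.2% = 14.8%.

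| Case, no true change | Shift to high | Any high value |
|---|---|---|
| Matched sessions | 20.1% | 33.4% |
| q = 2/3, d = 0.2 | 14.8% | 27.0% |
| q = 2/3, d = 0.3 | 12.8% | 24.2% |
| q = 2/3, d = 0.5 | 9.9% | 19.6% |

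With an assumed true rise of 0.3 mmol/L, the shift share is 36.2% when matched and 25.4% at q = 2/3, d = 0.3. At q = 1, d = 0.3 it is 20.1%, the same as with no rise at all.

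**The case against.** The strongest reply is that footnote 1 permits later sessions but does not require them. If sites keep these visits at the first session, the bias is zero. The documents contain no potassium value by session, and no mean, SD or upper limit. That stands: the direction is probable, and the size is conditional.

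A reader might infer that the baseline is always a first-session sample. The documents do not say so. SAP 4.8.2 says typically, SAP 4.1.2 admits unscheduled values, and Protocol 8.4.1 puts Day 1 only preferably on the first session of the week.

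A reader might also infer that every open-label potassium change is biased, or that the tables would conceal hyperkalaemia. Neither is supported:
- The open-label end-of-treatment chemistry includes potassium and is taken at the first dialysis of Week 15. The end-of-period shift, and the last post-baseline value for completers, are matched on the planned schedule. An early terminator's last value may not be.
- Actual values are summarised beside changes, classes use the absolute reference range, and all abnormal values are listed (SAP 4.8.2). A shift from normal to pathological must be reported as an adverse event (Protocol 10.5.4).
- The placebo-controlled potassium comparison comes from the double-blind period, which is session-matched.

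These safeguards are real but partial. Listings and laboratory-triggered adverse events draw largely on the same samples, and a short-gap value below the limit is neither listed as high nor counted as a shift.

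Extending the point to vital signs is tempting but not supported. Their baseline is typically open-label Day 1 (SAP 4.8.4), not the Day 85 laboratory sample, and nothing in the documents gives a direction or size for a session effect.

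**Conclusion.** The point holds for the interim potassium rows, Weeks 2 to 12, of the change and shift tables. These compare draws from any session with a baseline that is typically from the first session, and no planned analysis separates timing from treatment. The bias is about -0.13 to -0.40 mmol/L if the gap effect is 0.2 to 0.6 mmol/L, sessions are chosen evenly and the baseline follows the 3-day gap. It vanishes if sites keep to the baseline session or if there is no gap effect, and it reverses for subjects whose baseline follows a 2-day gap.

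This is a cheap improvement to descriptive safety tables. It touches no efficacy conclusion and does not show that hyperkalaemia would be missed.

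**What to change.** **Schedule.** In Table 2, footnote 1, and in 8.7.2 to 8.7.7, plan the open-label potassium draw for the first dialysis of the scheduled week, or else for the same session of the week as the subject's baseline sample, following the rule in 9.3. No extra visit or sample is needed. The cost is less scheduling flexibility for sites.

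**Data already collected.** Keep the planned tables. Add to SAP 4.8.2 a supportive potassium change and shift summary limited to draws at the same session as baseline, or presented by session. SAP 4.6 shows that the open-label dialysis eCRF page labels time points by week and by order of session within the week, so the session should be derivable by matching dates. Days since the previous dialysis would also handle subjects whose study week does not start at the first session of the calendar week. For the Day 85 baseline, the previous dialysis has to come from the double-blind records. The cost is some programming and fewer values: with an even spread, about one third of the interim draws would remain in the matched summary.

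Leave vital signs out of this change. If the sponsor wishes to include them, tie them to the session of the open-label Day 1 baseline.

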4.1.2 Definition of Baseline, Visits and Visit Windows

In general, the baseline is defined as the last available (non-missing) value (scheduled or unscheduled) prior to the first dose in the open-label extension period. For the efficacy endpoints, the 5-D itch scale and the Skindex-10 scale score, analyses will be conducted based on two different baseline definitions. The first definition is that baseline is the last available (non-missing) value (scheduled or unscheduled) prior to the first dose in the open-label extension period. The second definition is that baseline is the last available value (scheduled or unscheduled) before or on the same day as randomisation or if missing as any values during Week 1 (\leq Day 7). As a general rule for safety and efficacy related summaries (e.g., tables), the visit label mentioned in [Table 3](#) will be used to present the corresponding data by study visits for the open-label extension period.

Table 3: Study Visits and Planned Assessment Window for Safety and Efficacy Analysis

Visit	Visit Label	Planned Target Day (Assessment Time Window) for by visit parameters
EoT (Double-blind) / Day 1 (Open-label)	Baseline (Open-label)	Day 1 (\leq Day 1) ^a
Week 2 (Open-label)	Open-label Week 2	Day 8 to Day 14 (Day 8 to Day 21)
Week 4 (Open-label)	Open-label Week 4	Day 22 to Day 28 (Day 22 to Day 35)
Week 6 (Open-label)	Open-label Week 6	Day 36 to Day 42 (Day 36 to Day 49)
Week 8 (Open-label)	Open-label Week 8	Day 50 to Day 56 (Day 50 to Day 63)
Week 10 (Open-label)	Open-label Week 10	Day 64 to Day 70 (Day 64 to Day 77)
Week 12 (Open-label)	Open-label Week 12	Day 78 to Day 84 (Day 78 to Day 91)
EoT/ET (Open-label)	Open-label Week 14	Day 99 (Day 92 to maximum day of [Day EoT/ET visit and Day 99])
	Last Post-baseline (Open-label) ^b	
Follow-up (Open-label)	Follow-up (Open-label) ^c	EoT/ET visit + 7 Days ([EoT/ET visit + 1] to maximum day of [EoT/ET visit + 10, 109])

^a Study Day 1 is defined as the first dose date during the open-label extension period (as per the “Study Drug Administration- Open Label” eCRF page).

^b The last post-baseline visit is defined as the latest value recorded for a given parameter, not including the Follow-up Visit or any visits following the End of Treatment/Early Termination Visit. To be displayed for safety endpoints summary tables.

^c Follow-up (Open-label) is applicable for safety analysis only.

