4.1.3 Planned Assessment Windows

Assessments collected by study week that are collected at early termination visit and unscheduled visits will be assigned to a planned visit window. If the early termination or unscheduled visit day falls into an assessment time window, it will be mapped to the corresponding scheduled analysis visit. Should more than one measurement fall within a visit window, priority is given first to the measurement with a non-missing value in the following order: first, the scheduled assessment; second, an early termination visit; and next, the unscheduled assessment closest to the planned day. In the case that two unscheduled visits are equidistant, the latest will be used. This rule will be applied both to efficacy and safety endpoints. For detailed assessment time window information, please see the above [Table 3](#).

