4.8.4 Vital Signs Evaluations

Summary tables for vital signs include descriptive statistics for baseline and each post baseline assessment including last post-baseline measurement. Descriptive statistics are calculated by treatment sequence and all sequences pooled on both the actual values and the change from baseline for Body Temperature, Sitting Respiratory Rate, Sitting Radial Pulse Rate, Sitting Systolic Blood Pressure and Sitting Diastolic Blood Pressure.

Baseline is defined as the last measurement taken on or prior to the first day of open-label dosing. This will typically be Day 1 of the open-label extension period (prior to treatment).

All vital signs will be listed in a by-subject listing and will be sorted by subject identifier and date of assessment.

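### Open-label heart rates recorded only when clinically significant are not kept out of the SAP's by-visit pulse summaries

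*Protocol*

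**What the plan says.** **Recording.** Protocol Table 2, footnote 8 (open-label period) states: "Heart rate will be measured at each dialysis". Outside the scheduled visits the value is to be entered in the eCRF only "if the heart rate is clinically significant at visits outside the pre-specified visits per Schedule of Events". The SAP repeats this footnote under its own Table 2.

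**Schedule.** The synopsis (Procedures, Open-label Extension Period) says: "Vital signs will be monitored on Day 1, at Week 4, Week 8, Week 12 and at the end of treatment or early termination visit". Protocol Table 2 and Sections 8.7.2, 8.7.4 and 8.7.6 plan no vital signs at Weeks 2, 6 or 10.

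**Windows.** SAP Table 3 (Section 4.1.2) gives one grid for safety and efficacy. For Week 2 it reads "Day 8 to Day 14 (Day 8 to Day 21"). Week 6 takes Days 36 to 49 and Week 10 takes Days 64 to 77.

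**Mapping.** SAP 4.1.3: "If the early termination or unscheduled visit day falls into an assessment time window, it will be mapped to the corresponding scheduled analysis visit". Among non-missing values in a window the order is "first, the scheduled assessment; second, an early termination visit; and next, the unscheduled assessment closest to the planned day". The section applies this to safety as well as efficacy endpoints.

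**Summary.** SAP 4.8.4 tabulates "descriptive statistics for baseline and each post baseline assessment including last post-baseline measurement" for sitting radial pulse rate and the other vital signs. It has no exclusion for unscheduled readings. SAP 4.1.2 also lets an unscheduled value serve as baseline.

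**The concern.** A heart rate that is stored because it was judged clinically significant has been selected on its own value. Such readings are useful as a count of events, but they cannot be averaged as though they were a sample of the subjects' heart rates at that visit. The SAP's general rule for unscheduled values makes no such distinction. At Weeks 2, 6 and 10 there is no scheduled vital-sign value to take priority over them.

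Tachycardia and palpitations are adverse events of special interest (Protocol 10.8.4.1), so the pulse table will be read with some care. A mean that moves at alternate visits because of the recording rule could be mistaken for a drug effect or could obscure one. SAP 4.8.2 gives laboratory data shift tables and a separate listing of abnormal values. SAP 4.8.4 plans neither for vital signs, so the clinically significant readings have no count of their own in the vital-sign outputs.

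**Working it through.** The plan states no figure on this point, so there is none to reproduce. The check traces the rules and then asks how far the composition of a row can be pinned down.

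**1. What can enter each row of the pulse table**

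- *Weeks 2, 6 and 10.* No scheduled vital signs exist. The possible sources are early-termination readings (taken whatever the result, and ranked above unscheduled ones), scheduled visits that drift out of window, ad hoc checks, and the conditional heart rates. The three windows span 14 + 14 + 14 = 42 of the 14 × 7 = 98 open-label days.
- *Weeks 4, 8 and 12.* A non-missing scheduled value takes priority. A conditional reading enters only if that value is missing and there is no early-termination value.
- *Baseline.* This is normally the pre-dose Day 1 value. A conditional reading can matter only if that value is missing.
- *Last post-baseline.* This is normally the end-of-treatment or early-termination value. A conditional reading can matter only if that value is missing.

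**2. Is this heart rate the tabulated pulse?** Footnote 8 lists heart rate among the vital signs. It can hardly mean the ECG heart rate, because open-label ECGs are scheduled only at the end-of-treatment or early-termination visit. Radial pulse is the only rate among the vital signs in Protocol 9.2 and SAP 4.8.4. On the other side, SAP 4.8.3 uses the term heart rate for an ECG parameter, Appendix 2 lists radial pulse rate and heart rate separately, and no eCRF field or visit label is named for the conditional readings. That they enter the pulse table is therefore a strong inference and is not explicit.

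**3. Composition of a Week 2, 6 or 10 row (assumed inputs)**

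The documents give none of these rates. Assumptions: N = 200 open-label subjects; a proportion d = 2% to 15% terminating early, spread evenly over 98 days; a probability p = 0.1% to 2% per dialysis of a clinically significant heart rate; 3 × 2 = 6 dialyses per window. Out-of-window and ad hoc visits are ignored.

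- Early-termination readings: E = N × d × 14/98
- Subjects with a conditional reading: C = (N − E) × [1 − (1 − p)^6]
- Selected share: C / (E + C)

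Example with d = 5% and p = 0.5%: E = 200 × 0.05 × 14/98 = 1.43; C = 198.57 × (1 − 0.995^6) = 198.57 × 0.0296 = 5.88; share = 5.88/7.31 = 80%.

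| Early termination (d) | p = 0.1% | p = 0.5% | p = 1% | p = 2% |
|---|---|---|---|---|
| 2% | 68% | 91% | 95% | 98% |
| 5% | 45% | 80% | 89% | 94% |
| 10% | 29% | 67% | 80% | 89% |
| 15% | 21% | 58% | 73% | 84% |

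Across the grid, (E + C)/N runs from 0.9% to 13.3%, so a row describes about 1% to 13% of subjects.

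**4. Direction of the bias.** Footnote 8 does not define clinically significant, so low rates may qualify too. As an illustration only, suppose heart rates are normal with mean 76 and SD 11. The mean of the selected readings is then 103.9 if only rates above 100 qualify, 81.8 if rates below 50 or above 100 qualify, and 53.1 if rates below 50 or above 110 qualify. Neither the size nor the sign of the bias can be fixed from the documents.

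**The case against.** The strongest case against the point has several parts.

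- *The link to the pulse table is not written down.* This stands. The point is conditional on it, although it remains the likelier reading.
- *Table 3 is a shared grid.* Weeks 2, 6 and 10 are there because potassium is scheduled then, SAP 4.1.3 speaks of a corresponding scheduled analysis visit, and the table shells may print no vital-sign rows for those weeks. This is possible, but the SAP text does not say so, and the substitution for missing scheduled values would remain.
- *The rows would look sparse.* SAP 4.1.1 prints the numbers of subjects with and without a value, so a careful reader would notice. That limits the harm but does not make the mean interpretable.
- *Safety is covered elsewhere.* Protocol 10.5.6 requires clinically significant vital signs to be reported as adverse events, SAP 4.8.1 tabulates the events of special interest, and Listing 16.2.9.3 holds all vital signs. This stands, and it keeps the consequence small.

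Three stronger readings are tempting, and the documents do not support them:

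- A reader might infer that the Week 2, 6 and 10 rows must be almost entirely abnormal. Early-termination values share those windows with higher priority, and the share depends on rates the documents do not give.
- A reader might infer that abnormal readings at Weeks 4, 8 and 12 are hidden. Preferring the scheduled value is the unselected choice, and the other readings remain in the listing and the adverse-event data.
- A reader might carry the point over to the double-blind period, since Protocol Table 1, footnote 6 has the same condition ("if heart rate is clinically significant at visits outside the pre-specified visits per Schedule of Events"). That period has its own SAP, which was not supplied, and its vital signs are scheduled every two weeks from Day 15, so the same empty windows are not shown.

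**Conclusion.** The point holds as a gap in the SAP. The stated rules admit heart rates selected for being clinically significant into by-visit vital-sign summaries, and no text keeps them out. The main exposure is at open-label Weeks 2, 6 and 10. A secondary exposure arises wherever the scheduled Week 4, 8 or 12, baseline or last post-baseline value is missing.

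This rests on one assumption about the eCRF, namely that the conditional readings are stored as vital-sign pulse rate. Given that, the means and changes in the affected rows would be biased and drawn from a small subset of subjects. The percentages under working show only how widely the answer moves with assumed rates; they do not estimate the bias. No figure in beats per minute can be attached to it.

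The effect is confined to a descriptive safety table in an uncontrolled extension. It touches neither the primary endpoint nor the adverse-event tables. It deserves a short correction because the correction is cheap.

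**What to change.** State in SAP 4.1.3 and 4.8.4 that baseline, by-visit and last post-baseline summaries of vital signs use scheduled and end-of-treatment or early-termination assessments only, and that heart rates recorded conditionally under Table 2, footnote 8 are excluded from them. The Week 2, 6 and 10 vital-sign rows would then be empty or hold early-termination readings only.

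Report the conditional readings as what they are: the number and percentage of subjects with at least one clinically significant heart rate, by treatment sequence and pooled. Keep the individual values in the existing vital-signs listing (16.2.9.3). State which eCRF field and visit label hold them, so that the exclusion can be programmed and the open question about pulse rate is settled.

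The cost is one sentence in the SAP and one count row in a table. No new data are needed.
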